8.3.5 Dose Specifics

The administered activity will be 0.07 mCi/kg with a maximum of 5 mCi. The amount of injected drug is $\leq 6.1 \mu\text{g}$ ($\leq 25 \text{ nmol}$ per dose) of FLT.

8.3.6 Preparation

The injectable activity of FLT for most studies will be $\leq 0.07 \text{ mCi/kg}$ of fluorine-18, not to exceed 5 mCi with a specific activity greater than 200 Ci/mmol at the time of injection. In the dose of FLT, only a small fraction of the FLT molecules are radioactive.

8.3.7 Route of Administration
FLT is administered to subjects by intravenous injection. There is no evidence that nonradioactive and radioactive FLT molecules display different biochemical behavior.

8.3.8 Incompatibilities
N/A

8.3.9 Availability

Rev Add2 8.3.9.1 Drug Ordering
¹⁸F-FLT will be supplied by approved manufacturing sites under the ECOG-ACRIN IND. The manufacturing site (supplier) and receiving site including site personnel must meet all requirements and training qualifications as outlined in Sections [4.3.3](#) & [4.3.4](#). A list of approved manufacturing sites can be found on the CTSU website, on the EA6183 protocol page under the “Miscellaneous” tab.

For those sites designated as on-site manufacturing, [F-18] FLT chemistry manufacturing and control procedures must be filed with and approved by ECOG-ACRIN IND. For additional information about on-site manufacturing, contact [name] at [contact].

The ordering of ¹⁸F-FLT should be done with a written order from the responsible authorized user, and administration of ¹⁸F-FLT should be performed by the authorized user or a qualified staff member under the authorized user's supervision (e.g. nuclear medicine technologist). Institutions should follow institutional practice for the injection of investigational radiopharmaceuticals.

All approved manufacturing sites may only deliver to another site if delivery of tracer is completed within the stability time limit. Manufacturing sites may release the ¹⁸F-FLT to a commercial radiopharmacy shipper once it passes all quality control testing (excluding sterility).

8.3.9.2 Drug Returns
If for any reason the study imaging is unable to be completed, sites will allow the radioactivity of the FLT solution to decay and then discard it appropriately per site's policies and procedures. A copy of the policy should be available upon request.

8.3.9.3 Drug Accountability
The investigator or the investigator-designee must maintain a detailed record of receipt, disposition, and destruction dates of FLT solution, using the Drug Accountability Record form available through CTSU.

In accordance with regulations, the radioisotope vendor conducts several quality control tests on the FLT product

prior to release for human administration. Once delivered to the participating institution, doses will be stored in the appropriate storage area in the nuclear medicine facility until they are administered to the patient.

https://ctep.cancer.gov/forms/docs/agent_accountability.pdf

8.3.10 Side Effects

There is a chance of a rare but serious allergic reaction to the FLT.

8.3.11 Nursing/Patient Implications

Standard safety precautions required when handling radioactive materials, predominantly during the injection and uptake period should be followed. FLT requirements are similar to those used for other PET tracers, such as FDG.

9. Statistical Considerations

9.1 Study Design and Objectives

In this phase II study, patients with resectable locoregional metastases from cutaneous or unknown primary melanoma (Stages III N1B/C/D) will be enrolled. The primary objective is to evaluate the pCR rate for the neoadjuvant combination of encorafenib and binimatinib. It is hypothesized that this combination of treatment will yield at least 57% pCR rate. Simon's two-stage design will be used, enrolling with up to 42 patients (for 39 evaluable).

Evaluable patients are defined as eligible patients (per Section [3](#)) who receive at least one dose of neoadjuvant therapy with encorafenib and binimatinib and are resectable at enrollment. The likelihood of progression, delay in resection or failure to proceed to surgery during the neoadjuvant period is expected to be very low. Therefore, we expect at least 39 out of 42 patients will be evaluable.

All patients who receive at least one dose of neoadjuvant therapy will be included in the 15 patient-cohort that will trigger the interim analysis.

Secondary clinical endpoints include: i) to evaluate clinical response rate (RR), DFS, OS, ii) to assess correlation of pCR with RR, DFS, OS, iii) to assess safety and toxicity iv) to evaluate CD8+ T cell infiltration in tumor or tumor bed pre, during and post neoadjuvant treatment and the change in CD8+ TIL with neoadjuvant treatment and correlate with clinical response, and v) to compare local review for pathologic response with central pathology review. Secondary imaging endpoints are addressed in Section [9.7](#).

9.2 Study Endpoints

Of the 42 patients accrued, we expect at least 39 patients will be evaluable. The main analysis for clinical endpoints will be based on 39 evaluable patients. Based on prior studies, it is not expected that there will be significant issues with disease progression or severe toxicities that interfere with planned surgical resection.

A pCR will be defined as the absence of residual viable melanoma in the resected metastasis site as assessed on local pathology review.

Overall Survival (OS) will be defined as the time from enrollment to death from any cause. Patients who have not died will be censored at the date last known to be alive. Disease-Free Survival (DFS) will be defined as the time from complete surgical resection to disease progression or death (whichever occurs first). Patients who are not eligible for resection will not be included in this analysis. Cases who have not had an event will be censored at the date of last disease assessment documenting the patient was free of progression. Progression will be evaluated based on international criteria proposed by the revised Response Evaluation Criteria in Solid Tumors (RECIST) guideline (version 1.1) as described in Section [6](#). Response will be defined by the RECIST guidelines (version 1.1) as described in Section [6](#). Toxicity will be defined using the CTCAE.

Ki-67 IHC in tumor cells will be graded as a percentage of total number of tumor cells with nuclear staining (to the nearest 10%) over 10 high powered fields (at 20X magnification).

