define each holdout subject as test positive ($>$ threshold) vs. test negative (\leq threshold). This step will be repeated until every subject has been a holdout and has test result (positive/negative) defined. Sensitivity and specificity will then be calculated and reported, using the test result for each subject defined during holdout.

The proposed sample size of 42 patients (34 analyzable), assuming a pCR rate of 57%, yields a minimum of 81% power to reject the null hypothesis of an uninformative marker (ROC AUC=0.5) based on a one-sided test with type I error rate of 0.05, assuming the true ROC AUC is 0.74 or higher (PASS 2019).

In addition, estimates of diagnostic performance will be reported for percent change in ^{18}F -FLT PET/CT SUVpeak.

This analysis will be repeated separately for post-neoadjuvant ^{18}F -FLT PET/CT uptake.

Secondary imaging aim #3: To assess the correlation between change in ^{18}F -FLT PET/CT uptake and change in Ki-67.

This secondary imaging aim consists of assessing the correlation between the anticipated decrease in ^{18}F -FLT PET/CT (from the baseline scan to the post-neoadjuvant scan) and the change in tumor cell Ki-67 (from baseline to post-neoadjuvant therapy).

The correlation between percent change in continuous SUVmax and percent change in the continuous Ki67 score will be estimated using the Spearman correlation coefficient. A one-sided correlation test with null hypothesis of zero correlation will be conducted at alpha level of 0.05. The corresponding confidence interval for the estimated Spearman correlation coefficient will also be reported.

The proposed sample size of 42 patients (34 analyzable) yields a minimum of 83% power to detect a nonzero correlation, assuming that the true correlation is 0.5 or higher. A two-sided Spearman correlation test with a type I error rate of 0.05 was used for this computation based Monte Carlo simulation ($n=100,000$) from a bivariate normal distribution (PASS 2019).

Correlation between change in ^{18}F -FLT PET/CT and the early change in tumor cell Ki-67 (from baseline to the week 2 interim biopsy) will also be separately estimated; however, as the week 2 interim biopsy is not mandatory, we expect small numbers of subjects, and thus this analysis will be exploratory. The corresponding correlation with percent change in ^{18}F -FLT PET/CT SUVpeak will also be reported.

10. Specimen Submissions

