11.2 Ki67 and CD8+ infiltration

CD8 and Ki67 assays including staining, digital imaging and image analysis will be performed at MD Anderson Cancer Center and final result analysis will be performed under the direction of [name].

CD8 will be quantified as an H score as proposed and will include cytoplasmic and membranous staining. Focus will be placed on the tumor and peritumoral areas if needed and these areas of interest will be designated by the pathologist.

Ki67 nuclear staining is considered positive and not graded by staining intensity. The positively stained cells will be enumerated and the score will be generated by assessing both the total number and density of positive cells per square millimeter within the tumor/tumor bed area.

Ki-67 IHC in tumor cells will be graded as a percentage of total number of tumor cells with nuclear staining (to the nearest 10%) over 10 high powered fields (at 20X magnification).

Ki-67 alone can highlight any proliferating cell so this may overestimate the percent of proliferating cells. Focus will be placed on the on tumor cell rich areas as designated by pathologist.

Ki-67 IHC

Immunohistochemical studies will be performed on a Leica Bond autostainer, using the following antibodies: 3,3'-diaminobenzidine chromogen anti-Ki-67 (clone MIB-1; Dako, Carpinteria, CA; dilution 1:100).

CD8 IHC

Immunohistochemical studies will be performed on a Leica Bond autostainer, using the following antibodies 3,3'-diaminobenzidine chromogen anti-CD8 (Life Sciences Technologies MS457s; 1:25).

Image Analysis

Slides will be scanned at 20x magnification (Aperio Scanscope AT Turbo; Leica Biosystems). Image analysis software (Aperio ImageScope) measures the number of positive cells within designated areas. A Nuclear v9 algorithm is applied to determine Ki67 positivity. Also, given the relatively small size of immune cells, a modified version of the Nuclear v9 algorithm will be applied as a basis for CD8 immune marker positivity, with the intensity thresholds adjusted manually to remove background artifacts and to account for variable differences in cell size.

For each region of interest designated, the numbers of positive cells will be tabulated, and the total number of positive cells will be divided by the total area (mm^2) in which cells will be counted. The result will be reported as number of IHC+ cells/ mm^2 .

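### Imaging aim #3 analyses percent change in a continuous Ki-67 score, but the plan grades Ki-67 in 10-point steps and also per mm², and does not say which scale is used

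*Combined protocol and SAP*

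**What the plan says.** Section 9.2 (Study Endpoints) gives one definition: "Ki-67 IHC in tumor cells will be graded as a percentage of total number of tumor cells with nuclear staining (to the nearest 10" percent), read over ten high-power fields. Section 11.2 repeats it.

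Section 11.2 also describes a second measure. There, "the score will be generated by assessing both the total number and density of positive cells per square millimeter within the tumor/tumor bed area". Slides are scanned, "A Nuclear v9 algorithm is applied to determine Ki67 positivity", and positive counts are divided by the area counted: "The result will be reported as number of IHC+ cells" per mm².

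Section 9.7.3.2, secondary imaging aim #3, concerns Ki-67 in tumour cells. Its correlation between percent change in SUVmax and "percent change in the continuous Ki67 score will be estimated using the Spearman correlation coefficient". The test is specified as follows: "A one-sided correlation test with null hypothesis of zero correlation will be conducted at alpha level of 0.05". The power statement is 83% for 34 analyzable patients and a true correlation of 0.5, from a two-sided 0.05 Spearman test simulated on bivariate normal data.

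The documents give no baseline Ki-67 distribution. They state no rule for a zero baseline, for ties, or for a resection specimen without viable tumour cells.

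**The concern.** A grade in 10-point steps is not continuous, and it is a different quantity from a count per area. One has tumour cells as its denominator; the other has square millimetres of tumour or tumour bed. The two can move differently on the same pair of slides, and the analyst would have to choose between them after the data exist.

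The choice matters in two ways. Coarse grading creates ties and distorts percent change most where the baseline is low, which weakens a rank correlation. The choice can also decide who is analysed: after a pCR there are no viable tumour cells to form a percentage, whereas a density over the tumour bed can still be counted. Section 9.7.1 presents this correlation as possible evidence that FLT-PET truly measures proliferation. A null result on coarse data could not be told apart from a measurement artefact.

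**Working it through.** **Inputs from the documents.** n = 34 analyzable, true correlation 0.5, one-sided alpha 0.05 for the planned test, two-sided 0.05 for the power figure, stated power 83% (all 9.7.3.2); 10-point grading (9.2, 11.2); pCR rate 57% (9.7.3.1).

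**Assumptions, because the documents are silent.** Five baseline Ki-67 distributions: uniform 20-90%, uniform 5-80%, and lognormal with median 30% (log SD 0.6), 20% (0.7) or 10% (0.7), capped at 95%. Three distributions of the Ki-67 fall, as mean/SD: 50/20, 50/30 and 40/40. The SD of 20 is borrowed from the SUVmax assumption in 9.7.3.1.

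**Step 1: reproduce the plan's figure.** Draw 100,000 bivariate normal samples of 34 with correlation 0.5. Compute the Spearman coefficient r and t = r·√[(n − 2)/(1 − r²)], and compare with the t distribution on 32 degrees of freedom.
- Two-sided 0.05: 82.3%, against the stated 83%. The figure reproduces.
- One-sided 0.05, the test actually planned: 89.4%. The stated figure is therefore conservative in this respect.

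Both results are for data without ties.

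**Step 2: what 10-point grading does to percent change.** Change = (baseline − post)/baseline.
- Baseline below 5% is graded 0, so the denominator is 0 and the change is undefined.
- Baseline from 5% to under 15% is graded 10. After a fall, the post value is graded 10 or 0, so the change is (10 − 10)/10 = 0% or (10 − 0)/10 = 100%. As an illustration, a fall from 14% to 6% is really (14 − 6)/14 = 57% but is recorded as 0%. A fall from 14% to 4% is really 71% and is recorded as 100%.

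**Step 3: effect on power.** Same model. Baseline and post values are each rounded to 10 points, change is recomputed, and patients with a graded baseline of 0 are dropped. There were 8,000 runs per scenario; ranges are over the three assumed falls.

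| Assumed baseline | Undefined change | One-sided power, 10-point grade | Two-sided power, 10-point grade |
|---|---|---|---|
| Uniform 20-90% | 0% | 86-88% | 77-80% |
| Uniform 5-80% | 0% | 76-84% | 65-76% |
| Median 30% | about 0.2% | 76-84% | 65-75% |
| Median 20% | 2.4% | 64-79% | 51-69% |
| Median 10% | 16% | 45-67% | 33-55% |

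Without rounding, power is about 82% two-sided and 89-90% one-sided in every row. Recording to the nearest 1% never gave less than 87% one-sided or about 80% two-sided, so the width of the step causes the loss. Setting negative post values to zero changes these figures by about a point or less.

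**Step 4: specimens with pCR.** 0.57 × 34 = 19.4, so about 19 of 34 patients would have no viable tumour cells at surgery, leaving 34 − 19 = 15.
- If those 19 are all assigned a 100% fall, the ties alone bring one-sided power to about 82%, even on an unrounded score.
- If they are dropped, 15 pairs give about 56% one-sided.

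This is separate from the rounding, but it means that naming a scale without a rule for these patients would not be enough.

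**The case against.** The best defence is that aim #3 may never use the 10-point grade. It refers to a continuous score, and in section 11.2 the word score is attached to number and density per mm², which has no rounding loss. This has weight, but it does not settle the matter. The same aim is about Ki-67 in tumour cells, only the percentage is defined on tumour cells, and the percentage is the only Ki-67 definition in the endpoints section. The text supports both readings.

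A second defence concerns size. Section 9.7.3.1 expects melanoma to be more proliferative than the breast cancers studied earlier. If baselines are 20% or higher, one-sided power on the 10-point grade is 86-88%, still above the stated 83%. This stands, and it limits the claim.

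Third, section 11.2 acknowledges that Ki-67 marks any dividing cell and directs the count to areas rich in tumour cells chosen by the pathologist. That partly answers the worry that a density counts lymphocytes in a node.

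Fourth, a reader might infer that the laboratory already holds an exact tumour-cell percentage and discards it by rounding. Section 11.2 does not show this: the software is described as counting positive cells per area, with no count of all tumour cells.

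Finally, section 9.7.3 places all the imaging aims as secondary to the main trial. No treatment decision depends on this one.

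**Conclusion.** The inconsistency is certain: two Ki-67 scales, one graded in 10-point steps, feed an analysis that calls its variable continuous and names neither. The consequence is conditional. If the 10-point grade is used, one-sided power at 34 pairs and correlation 0.5 falls from about 89% to 86-88% when baselines are 20% or higher, and to 45-67% at a median baseline of 10%. This rests on assumed baseline distributions and assumed falls.

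Two stronger readings are tempting. One is that rounding by itself removes much of the aim's power. The documents do not support that as a fixed result, because they give no baseline distribution and do not say that the graded percentage is the variable analysed. The other is that percent change is undefined for low-baseline tumours in general. It is undefined only below 5%, which is 0% to about 16% of patients in the scenarios tried; from 5% to 15% it is defined but nearly uninformative.

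**What to change.** - **Sections 9.2 and 11.2:** replace the 10-point grading with recording to the nearest 1%, or unrounded where the image analysis yields a tumour-cell denominator.
- **Section 9.7.3.2:** name the one Ki-67 scale used for aim #3, and make the other a sensitivity analysis. Define Ki-67 change as (baseline − post)/baseline, the same direction as the SUVmax change in 9.7.3.1.
- **Also in 9.7.3.2:** state in advance how a zero baseline is handled, and how a specimen with no residual viable tumour cells is handled. For the latter, say whether pCR patients are assigned a full fall, analysed on density, or excluded, and give the number of pairs expected under that rule.

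The cost is wording in three sections, with no new patients, slides or assay. The downside is that a 1% reading implies somewhat more precision than a visual read has.

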9.3 Sample Size Considerations and Monitoring Plan

A Simon's optimal two-stage design will be used to allow for an interim analysis for futility. Accrual will be held during the interim analysis. Fifteen (for 14 evaluable) subjects will be enrolled and pCR will be assessed. If 5 or fewer subjects achieve a pCR, the trial will be stopped for futility. If greater than 5 subjects achieve a pCR, then the trial will enroll an additional 27 (for 25 evaluable) patients. If 18 or more subjects out of 39 total evaluable subjects achieve a pCR the study will be considered 'positive'. The study was designed to evaluate the pCR rate improving from 33% to 57%. This design provides 87% power with approximately one-sided type I error rate of 0.05 for the primary endpoint.

The hypothesis states that encorafenib with binimatinib will yield a pCR rate of 57%. The baseline pCR rate of 33% was estimated from published values as summarized in Table 1 in Section [1](#) and is thus the null pCR rate.

We anticipate an average accrual of 1-3 patients per month. The first stage analysis will occur when the first 15 patients have a pCR assessed. Under the null pCR rate of 33%, there is 70% chance of stopping the study after the first stage evaluation. Adverse events will be closely monitored during the study.

Interim safety analyses based on the first 15 patients will evaluate:

- Proportion of patients who develop progressive disease per RECIST 1.1 before surgery but proceed with surgical resection
- Proportion of patients who develop progressive disease per RECIST 1.1 before surgery and are unresectable
- Proportion of patients who develop toxicities that delay or prohibit surgery
- Surgical complications as defined by the operating surgeon as being related to surgery or oral therapy, at any point during follow up

We anticipate that the proportion of patients who experience any of the event listed in i) -iv) will be less than 15%. If at least one patient (out of 15 patients) experiences any of the event listed in i) - iv), the proposed treatment will be considered unsafe and the result will be discussed with the ECOG-ACRIN DSMC. The probability of observing at least one patient with the event in i) ii), iii) or iv) is 0.794 if the true event rate is 10% and is 0.913 if the true event rate is 15%.

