
deemed unresectable due to vessel encasement.[Blankenstein, Ann Surg, 2021]. Six patients required treatment interruption for toxicities but all completed neoadjuvant treatment. The pathologic responses included: pathologic CR in 28.6% (6/18), near pCR in 14.3% (3/18), pPR in 19% (4/18) and pNR in 23.8% (5/18). Radiologic response on CT or PET did not predict pathologic response. Surgical complications occurred in 80%, mainly seromas, wound infections, and lymphedema. Of these 18 patients who had surgery, 9 patients have recurred, including 6 with distant metastases. Five of the 6 patients with a pCR have not had a recurrence.

Of the 35 patients treated with Dabrafenib with Trametinib neoadjuvantly for 12 weeks in Long et al: 0/35 with clinical or radiologic PD before surgery (16 with CR, 14 with PR); all proceeded to surgery, Surgical complications (including infection requiring antibiotics, seroma, bleeding, lymphedema, thrombus) of any grade occurred in 63% (22) with 26% (9) being grade 3. Two patients stopped treatment before 12 weeks due to treatment related adverse events. Of the 14 patients treated with neoadjuvant Dabrafenib and Trametinib for 8 weeks in Amaria et al: 1 withdrew consent before starting treatment, one withdrew consent for surgery given partial response to oral treatment and 12 patients received surgery. No patients evidenced radiologic or clinical progression prior to surgery: 2 CR, 9 PR and 2 SD. In the 12 who had surgery, 7 had a pCR and 2 had a pPR, while 3 had a pathologic non-response (>50% viable tumor in surgical specimen). They reported no unexpected peri-operative or post-operative treatment-related toxicities, nor were there any treatment related delays in surgery.

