5.1.2 Surgical resection

The patient will proceed to surgical resection after neoadjuvant treatment

- Surgery should be performed as soon as possible after completing 8 weeks of therapy; it must be performed within 2 weeks of completing the 8 weeks of neoadjuvant therapy, assuming the patient has adequately recovered from protocol therapy and no other new sites of distant disease are evident and histologically confirmed as specified on post-treatment imaging.
- Resectability, as determined by a surgical oncologist or experienced melanoma surgeon, is necessary prior to registration.
- Surgery date should be arranged in advance.
- Neoadjuvant treatment duration (8 weeks) cannot be extended to accommodate surgery scheduling.

- Encorafenib and binimatinib will be stopped within 48 hours of planned surgery or at 8 weeks, whichever is sooner.
- If there are any reversible issues precluding surgery such as treatment related toxicities or unrelated medical issues, surgery may be delayed by an additional 2 weeks as needed.
- Encorafenib and binimatinib treatment time would not be extended beyond 8 weeks.
- Patients must be surgically managed with complete removal of all target site(s) of metastatic melanoma, i.e. complete lymph node dissection, as feasible by the treating surgeon at the time of surgery.
- If initial presentation with a primary melanoma with nodal metastases, wide local excision of the primary should be carried out per standard of care.
- If the residual target tumor is not visible on post-treatment imaging, surgical exploration and formal lymphadenectomy with excision of primary/ in transit lesions, if applicable, as per standard recommendations is required.
- The treating surgeon should attempt to mark the target lesion with a suture at the time of surgery to facilitate pathologic analysis.

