9.5 Statistical Analysis Plan

Efficacy endpoints will be analyzed in evaluable patients (as defined in Section 9.1. The primary endpoint of pCR rate will be estimated and 90% CI adjusting for the first stage analysis will be provided. OS and DFS distributions will be estimated using the Kaplan-Meier method. Median OS and DFS will be described with 95% confidence intervals. Clinical response rate (RR) (per RECIST 1.1) will be estimated with 95% confidence interval. Clinical data from unevaluable patients will be summarized separately.

Safety analyses will be conducted on all patients who received at least one dose of trial therapy (i.e., treated patients). Adverse events will be graded using the National Cancer Institute (NCI) Common Terminology Criteria for Adverse Events (CTCAE) version 5.0. All treatment-emergent and baseline adverse events and hematological/biochemical toxicities based on laboratory measurements, as well as drug related AEs, will be summarized by NCI CTCAE v. 5.0 worst grade. The incidence of deaths and treatment-emergent serious adverse events (defined as number of patients experiencing the AE divided by all treated patients) will be summarized. Also, the incidence of adverse events leading to discontinuation of investigational product and/or withdrawal from the study will be summarized and listed. Changes in the CD8 T cell infiltration in tumor or tumor bed pre-, during and post- neoadjuvant treatment will be assessed and summarized using the descriptive statistics. The change in CD8+ TIL between pre-and post-treatment will be compared among patients achieving a pCR vs. no pCR using the Wilcoxon rank sum test. The concordance of pCR assessed based on local review vs. central pathology review will be evaluated. Kendall's Tau test will be used for this comparison.

In the event of missing data, it will be assumed that the data will be missing at random and no imputation will be performed.

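### The interim safety rule counts surgical complications of any grade at any time, so its under-15% expectation conflicts with the protocol's own cited rates and its one-in-15 'unsafe' flag is likely to be set by routine surgical events

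*Combined protocol and SAP*

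**What the plan says.** Section 9.3 sets out an interim safety analysis of the first 15 patients. Four items are counted: (i) progression before surgery with resection still done, (ii) progression that makes the disease unresectable, (iii) toxicity that delays or prevents surgery, and (iv) "Surgical complications as defined by the operating surgeon as being related to surgery or oral therapy, at any point during follow up". The list is bulleted in the text available; surgical complications is the fourth entry.

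The plan then states: "We anticipate that the proportion of patients who experience any of the event listed in i) -iv) will be less than 15" percent. One affected patient out of 15 is enough to trigger the rule, in which case "the proposed treatment will be considered unsafe and the result will be discussed with the ECOG-ACRIN DSMC". The plan gives the chance of at least one affected patient as 0.794 at a true rate of 10% and 0.913 at 15%.

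Section 1.4 reports what earlier neoadjuvant dabrafenib/trametinib studies saw at surgery. In a 35-patient study, complications "of any grade occurred in 63% (22) with 26% (9) being grade 3". In a second study, "Surgical complications occurred in 80%, mainly seromas, wound infections, and lymphedema". A third reports only that nothing unexpected happened. The operation in this trial is comparable. Section 5.1.2 says: "Patients must be surgically managed with complete removal of all target site(s) of metastatic melanoma, i.e. complete lymph node dissection".

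**The concern.** Items i to iii are uncommon on the protocol's own evidence. Section 1.4 reports no progression before surgery in the two dabrafenib/trametinib studies of resectable disease, and Section 9.1 expects progression, delay or failure to reach surgery to be very rare. A ceiling of 15% and a one-event alert can be defended for those.

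Item iv is different in kind. A seroma or an infected wound after a node dissection is related to surgery, so the surgeon's relatedness judgement removes little. With no grade threshold and no window, each such event counts the same as a patient who became unresectable. If these events occur at anything like the cited rates, the composite will exceed 15% and the 'unsafe' label will follow from the mandated operation itself. The DSMC would receive a flag that is nearly always up, with no limit against which to judge whether surgical risk had changed.

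**Working it through.** **Inputs**
- Look size 15, trigger at one or more patients, expected composite rate below 15%: Section 9.3.
- Any-grade surgical complications 22/35 (63%), grade 3 9/35 (26%): Section 1.4, 12 weeks of dabrafenib/trametinib in resectable disease.
- 80% in a second study: Section 1.4, initially unresectable disease; no count is given for the 80%.
- Share of cited events that would occur before the look: not in the documents. One half and one quarter are assumed, to show a range.

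**Formula.** If each patient has an event independently with probability p, P(at least 1 of 15) = 1 − (1 − p)^15.

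**The plan's own figures**
- p = 0.10: 1 − 0.90^15 = 0.794
- p = 0.15: 1 − 0.85^15 = 0.913

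Both match Section 9.3, so the arithmetic is right. The question is which p belongs to item iv.

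**Item iv alone, at the cited rates**

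| Rate used | p | Expected patients in 15 | P(rule fires) |
|---|---|---|---|
| Grade 3, 9/35 | 0.26 | 15 × 0.26 = 3.9 | 0.989 |
| Any grade, 22/35 | 0.63 | 15 × 0.63 = 9.5 | above 0.999 |
| Second study | 0.80 | 15 × 0.80 = 12 | above 0.999 |

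With 14 rather than 15 patients operated on, the 26% row becomes 0.985.

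**Sampling error in the benchmark.** The exact 95% interval is 44.9% to 78.5% for 22/35 and 12.5% to 43.3% for 9/35. At the lower limits the rule fires with probability 0.9999 and 0.865.

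**Only part of the events seen by the look**
- Any grade, half: 0.5 × 0.63 = 0.315, probability 0.997. A quarter: 0.25 × 0.63 = 0.1575, probability 0.924.
- Grade 3, half: 0.5 × 0.26 = 0.13, probability 0.876. A quarter: 0.25 × 0.26 = 0.065, probability 0.635.

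Item iv as written is any-grade, and that rate stays above 15% even at a quarter (15.75%). A grade 3 reading would fall below 15% after either discount, but item iv does not state one.

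**Ability to discriminate.** At 26% the flag is raised with probability 0.989. At double that, 52%, it is 1 − 0.48^15, above 0.999. For the flag to be raised only 10% of the time the true rate would have to be 1 − 0.9^(1/15) = 0.7%.

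**The case against.** The strongest reply is that this is meant as a tripwire. The only stated action is discussion with the DSMC. The plan prints 0.794 and 0.913, so the high sensitivity is disclosed. In a 42-patient single-arm study a sponsor may want the committee to hear of any event, and the review will show counts as well as a flag. That stands as a defence of a one-event alert for items i to iii. It does not explain an under-15% expectation that includes item iv, or the word 'unsafe' for an event seen in most patients of a cited study.

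The second reply is that the benchmarks transfer imperfectly, and this also stands. The 63% and 26% come from 12 weeks of a different doublet, over a complication window the documents do not give. The 80% comes from disease that was unresectable at entry, whereas this trial requires resectability. The closest match on schedule and resectability, 8 weeks in resectable disease, gives no complication rate. This is why the range in the working matters: the lowest figure is 0.635.

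A reader might infer more than the documents support:
- *The rule stops the trial.* It does not; no stop is stated.
- *The look has no data cutoff.* Section 9.3 places the safety review directly after the sentence "The first stage analysis will occur when the first 15 patients have a pCR assessed", and the natural reading is one interim look.
- *Surgical events go unreported.* Section 9.5 says adverse events "will be summarized by NCI CTCAE v. 5.0 worst grade", and the Section 7.1 schedule includes an adverse-event assessment at surgery.

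**Conclusion.** The point holds as a defect in a stated rule. For item iv the under-15% expectation is contradicted by the rates in Section 1.4. The one-event trigger fires with probability 0.989 at the cited grade 3 rate and above 0.999 at the cited any-grade rate. These figures assume independent patients and that the cited rates apply here. If only a quarter to a half of the events occur before the look, the range is 0.924 to 0.997 for any grade and 0.635 to 0.876 for grade 3. It would therefore go too far to say the flag is certain to be raised in this trial. It is fair to say that, as worded, it is likely to be raised by ordinary surgical morbidity and would then tell the DSMC little.

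The printed 0.794 and 0.913 are correct for the rates they name. The consequence is a misleading label and a missing benchmark, not a wrongly halted trial. It should be corrected, and wording is enough.

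**What to change.** In Section 9.3:
1. Take surgical complications out of the one-event count.
2. Define them as CTCAE grade 3 or higher within a stated postoperative window, for example 30 days.
3. Report them to the DSMC as a count and proportion, against a separate limit that the sponsor sets from a stated baseline for that window, with the operating characteristics printed.
4. State that the under-15% expectation, 0.794 and 0.913 apply to items i to iii only.

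Two limits as illustration (binomial, n = 15). The 13% column is half the cited grade 3 rate, and the 26% column is that rate in full:

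| Discuss with the DSMC at | True rate 13% | 26% | 40% |
|---|---|---|---|
| 4 or more of 15 | 0.12 | 0.57 | 0.91 |
| 5 or more of 15 | 0.04 | 0.35 | 0.78 |

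The choice depends on the baseline the sponsor can justify. If 26% is the expected rate for the chosen window, 4 or more would still fire more often than not with nothing amiss.

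The cost is a change of text, with no added patients or visits. There are two drawbacks. The flag for surgical events becomes less sensitive. And because accrual is held during the interim analysis, waiting for patient 15 to complete the window may lengthen the hold slightly.
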